7.2 Inclusion Criteria

Patients may be included in the study if they meet all of the following criteria:

- (1) Patients ≥ 18 years of age at the time dated informed consent is obtained.
- (2) Female patients must be pre-menarchal, surgically sterile (had a documented bilateral oophorectomy and/or documented hysterectomy), postmenopausal (cessation of menses for more than 1 year), non-lactating, or, if of childbearing potential, a serum or urine pregnancy test with the results known prior to AdreView™ (Iobenguane I¹²³ Injection) administration is negative.
- (3) Patients willing and able to comply with all study procedures and a signed and dated informed consent is obtained before any study-procedure is carried out.
- (4) Heart failure NYHA class II or III for symptoms, patients with ischemic or non-ischemic heart disease, eligible for ICD implantation as per each site's standard of practice.
- (5) Non-ischemic dilated cardiomyopathy or ischemic heart disease of at least 3 months duration receiving guideline-directed optimal medical therapy.
- (6) $25\% \leq \text{LVEF} \leq 35\%$, performed within 3 months before or at time of enrolment, as measured by radionuclide ventriculography, or electrocardiogram [ECG]-gated SPECT myocardial perfusion imaging [MPI], or magnetic resonance imaging [MR], computed tomography [CT], or 3D or 2D echocardiography [Simpson's or multidisc method or equivalent only, M-mode echocardiography is not accepted].

In case LVEF measurement is performed within 3 months before enrolment, measurement should be performed at least 40 days after a hospitalisation for HF or acute coronary syndrome (including myocardial infarction), and to be valid, method of measurement should be in accordance with the protocol and the imaging exam should be made available to the Sponsor in digital format.

In case several valid LVEF measurements are available, the closest to enrolment will be used for inclusion determination.

- (7) Clinically stable HF in the medical judgment of the investigator (i.e., no significant changes in medication, no worsening of symptoms, no unscheduled visits to the doctor's office) for the past 30 days and no hospitalisation for HF or acute coronary syndrome (including myocardial infarction) in the past 40 days.
- (8) Reasonable expectation of meaningful survival for at least 1 year.

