7.3 Exclusion Criteria

Patients must be excluded from participating in this study if they meet any of the following criteria:

- (1) Patients with existing ICD or patient having an indication of ICD implantation for secondary prevention of SCD.
- (2) Hospitalisation for HF or for acute coronary syndrome in the previous 40 days.
- (3) Patients where a cardiac resynchronisation therapy (CRT) is planned or indicated
- (4) Other indication for placement of device (sustained ventricular tachycardia, resuscitated sudden death, need for atrioventricular pacing).
- (5) NYHA class I or class IV symptoms at the time of study entry.
- (6) American College of Cardiology-American Heart Association (ACC-AHA) class III or class IV (unstable) angina.
- (7) Patient with chronic renal insufficiency defined as serum creatinine ≥ 3 mg/dl (or ≥ 265.2 μ mol/L).
- (8) Known or suspected hypersensitivity/allergy to Iobenguane or to any of the excipients in AdreView™ (Iobenguane I¹²³ Injection).
- (9) Patient who is pregnant or plans to become pregnant within 2 weeks after AdreView™ (Iobenguane I¹²³ Injection) administration.
- (10) Patient who has used any medication in the 2 weeks before AdreView™ (Iobenguane I¹²³ Injection) that could interfere with the test: e.g., but not limited to amitriptyline or derivatives, imipramine or derivatives, other antidepressants or drugs known or suspected to inhibit the norepinephrine transporter, antihypertensives that deplete norepinephrine stores or inhibit reuptake, sympathomimetic amines or cocaine.
- (11) Patients that have a medical condition that could interfere with the AdreView™ test (e.g., but not limited to left ventricular assist device, or prior heart transplant).
- (12) Patients who participated in a clinical study involving a drug or device within 30 days prior to study entry and patients participating in any other clinical study.
- (13) Patients having serious non-cardiac medical condition associated with significant elevation of plasma catecholamines, including pheochromocytoma.
- (14) Patients with a clinical diagnosis of (or being treated for) Parkinson's disease or Multiple System Atrophy.
- (15) The patient has participated in a research study using ionizing radiation in the previous 12 months.
- (16) Patients previously randomized in this study.

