8.5 Prior and Concurrent Therapy

Any medications taken by the patient within 30 days before and up to the end of study visit will be recorded in the eCRF along with the indication and dosage, including but not restricted to guideline-directed optimal medical therapy. Either the generic or the trade name may be recorded. The Sponsor/CRO will encode all therapy and medication according to a current well-recognised dictionary of medical codes.

Should any patients not be receiving guideline-directed optimal medical therapy at target dose per local guidelines, the investigator must document the reason(s) why in the source documents.

As stated in the exclusion criteria, patients will not be allowed to take any medications known or suspected to interfere with AdreView™ imaging as per Package Insert (or Summary of Product Characteristics or IB as applicable) for at least 5 half-lives prior to administration of AdreView™. The investigator will be responsible for assessing the patient's medication in order to determine whether the medication should be withdrawn for the required period. In the case of a patient requiring medications that can interfere with AdreView™ imaging and where the clinical status does not allow temporary withdrawal of the medication, the investigator may elect to withdraw the patient from the study on safety grounds.

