- b Recorded up to 30 days before screening. Investigators should record all guideline-directed optimal medical therapy. Should any patients not be receiving guideline-directed optimal medical therapy at target dose per local guidelines, the investigator must document the reason(s) why in the source documents.
- c A serum or urine pregnancy test will be performed for all women of childbearing potential.
- d Before vital signs are measured, the patient should be resting for at least 5 minutes. The same arm and position will be used each time vital signs are measured for a given patient and blood pressure will be measured from the arm contra-lateral to the site of AdreView™ administration whenever possible.
- e Acceptable methods of LVEF assessment are radionuclide or contrast ventriculography, ECG-gated SPECT MPI, MR, CT, or 3D 2D echocardiography (Simpson's or multidisc method or equivalent only). Image files will be sent to the Sponsor.
- f AdreView™ will be administered to all patients. First AdreView™ administration should be performed in the 15 (+7) days post-randomisation. For the low-risk cohort only, a second AdreView™ administration should be administered at 2 years (± 30 days) post-randomisation, unless patient withdraws prior to study termination or has already received an ICD. In this case the second AdreView™ scan will be offered before withdrawal becomes effective. Thyroid blocking should be performed before administration of AdreView™ in accordance with the Package Insert/Summary of Product Characteristics/IB and local regulations unless the patient has had a complete thyroidectomy.
- g At 3 hours 50 minutes after administration of AdreView™, patients will undergo a 10-minute acquisition of planar images, and whenever possible followed by SPECT acquisition, according to the imaging manual. Patients with LVEF 25% to 35% with an H/M ratio ≥ 1.6 will have a second AdreView™ scan at 2 years (± 30 days) post-randomisation.
- h Patients in the randomised AdreView™ group who are assessed as high risk, and patients in the SoC group according to the standard of care in each investigational site derived from the local implementation of internationally accepted HF guidelines. ICD implantation should be performed according to clinical practice and should be performed within 45 days after randomisation.

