9.3 Post-Randomisation Procedures

All female patients (unless pre-menarchal, surgically sterile or post-menopausal) will undergo a serum or urine pregnancy test on the day of and prior to AdreView™ administration. AdreView™ dosing will only commence if the result is negative.

AdreView™ will be administered to all patients.

The first AdreView™ administration should be performed in the 15 (+7) days post-randomisation. Starting at 3 hours 50 minutes after administration of AdreView™, patients will undergo a 10-minute acquisition of anterior planar images of the thorax, and whenever possible these will be followed by a SPECT acquisition. Details of the acquisition and transmission of images to the Sponsor are provided in the study Imaging Manual.

Only those patients allocated to the AdreView™ arm will have the results of the scan (H/M ratio calculated on an anterior planar image obtained at 3 hours and 50 minutes for 10 minutes, and with regions placed following the standard quantification method according to the Imaging Manual) available to make a decision on the need for implantation of an ICD. In patients allocated to the SoC group, the investigator will remain blinded to the results of the AdreView™ images and any information derived from them in order not to influence the decision to implant or not implant an ICD.

Patients in the AdreView™ arm who are deemed at high-risk for all-cause and cardiovascular mortality (H/M ratio <1.6 as defined in Section 6.1) will undergo ICD device implantation. ICD implantation should be performed within 45 days of randomisation. Patients deemed to be at low risk (H/M ratio ≥ 1.6 as per Section 6.1) will continue to receive guideline-directed optimal medical therapy but will not undergo ICD implantation. In the low risk group, a second AdreView™ scan will be performed at 2 years following the first scan, or in case of early withdrawal, prior to this withdrawal being effective.

Patients randomly allocated to the SoC group will undergo ICD implantation and will be managed and followed up in accordance with internationally accepted HF guidelines. ICD implantation should be performed within 45 days of allocation to the SoC group. The results of the AdreView™ scan will remain blinded to the investigator to avoid any influence regarding patient management. AEs, SAEs and AdreView™-emergent AEs will be recorded.

All data related to primary and secondary endpoints will be collected.

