4.1.1 Safety Analysis Set (Safety Population)

The safety analysis set comprises all patients who signed the informed consent form and met all of the inclusion criteria and none of the exclusion criteria.

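### SAP 4.1.2 filters the full analysis set on eligibility, against the protocol's all-randomised primary population, and inconsistent eligibility text makes that filter harder to apply

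*Protocol*

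**What the plan says.** **Analysis sets.** SAP 4.1.1 limits the safety set to consented patients who "met all of the inclusion criteria and none of the exclusion criteria". SAP 4.1.2 makes the full analysis set the randomised part of that safety set, so the eligibility condition carries over. SAP 5.4.1 bases the efficacy analyses on this set, and SAP 5.4.2 runs the primary non-inferiority test against 1.2. Protocol 12.2 defines the primary efficacy population as the patients randomised, with no eligibility condition. Protocol 12.2.1 adds that violations have no bearing on membership of either population. Protocol 7.4.1 and 9.6 describe the analysis as intention-to-treat and ask for mortality follow-up of all patients where possible.

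**Interfering medication.** Exclusion 10 (protocol 7.3) reads "Patient who has used any medication in the 2 weeks before AdreView™", followed by the kinds of drug meant. Section 8.5 begins "As stated in the exclusion criteria, patients will not be allowed to take any medications known or suspected to interfere with AdreView™ imaging" and then sets the period as "for at least 5 half-lives prior to administration of AdreView™".

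**LVEF method.** Inclusion 6 (protocol 7.2) requires LVEF "as measured by radionuclide ventriculography, or electrocardiogram [ECG]-gated SPECT myocardial perfusion imaging", or by one of several other methods. Contrast ventriculography is not among them, nor is it in section 9.1. Table 1 footnote e, in both the protocol and the SAP, says "Acceptable methods of LVEF assessment are radionuclide or contrast ventriculography", among others.

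**Timing.** Protocol 9.3: "The first AdreView™ administration should be performed in the 15 (+7) days post-randomisation".

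**The concern.** The primary comparison is protected by randomisation only if everyone randomised is counted in the assigned arm. An eligibility filter gives that up. It can be defended when eligibility is fixed before randomisation and judged the same way in both arms. Here the criteria are worded differently in different places, one of them refers to a moment after randomisation, and sites and patients know the arm (protocol 8.4). Removals therefore need not be balanced between arms.

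Interfering drugs also bear on the H/M value itself. That value decides ICD implantation in the AdreView arm and defines the H/M ≥1.6 subset for the first key secondary endpoint. The LVEF mismatch does not touch H/M. It matters only because LVEF method decides whether inclusion 6 is met, and hence who passes the SAP filter.

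**Working it through.** **1. The two population definitions**

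| | Protocol 12.2 / 12.2.1 | SAP 4.1.1 / 4.1.2 |
|---|---|---|
| Efficacy set | Randomised patients | Randomised patients who are also in the safety set |
| Eligibility condition | None | All criteria met |
| Effect of a violation | None | An eligibility violation removes the patient |

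A patient randomised in breach of one criterion is in the first set and not in the second. The SAP says it is based on protocol amendment 2 (SAP section 1) and gives no reason for the change.

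**2. The two medication windows**

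Exclusion 10 gives 14 days; section 8.5 gives 5 × half-life. They are equal when half-life = 14 / 5 = 2.8 days (67.2 hours). The documents give no half-lives, so these values are illustrative:

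| Assumed half-life | 5 half-lives | Fixed window | Longer rule |
|---|---|---|---|
| 1 day | 5 days | 14 days | 2 weeks |
| 2 days | 10 days | 14 days | 2 weeks |
| 2.8 days | 14 days | 14 days | equal |
| 4 days | 20 days | 14 days | 5 half-lives |
| 6 days | 30 days | 14 days | 5 half-lives |

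The rules differ on both sides of 2.8 days and neither contains the other. With a 1-day half-life and a last dose 7 days before injection, a patient satisfies 8.5 and fails exclusion 10. With a 4-day half-life and a last dose 16 days before, the reverse holds.

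**3. The LVEF lists**

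Inclusion 6 and section 9.1 agree with each other. Footnote e is wider, and the SAP reprints it. Inclusion 6 also makes an earlier measurement valid only if its method accords with the protocol. Because that clause points to the protocol as a whole, footnote e cannot simply be ignored.

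**4. Timing of exclusion 10**

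Latest scheduled first scan: 15 + 7 = 22 days after randomisation. The 14 days before a day-22 scan run from about day 8 to day 22, wholly after randomisation. On its wording, exclusion 10 can therefore be triggered by a drug first taken after the arm is known.

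**5. Size**

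The plan's event count first. With log hazard ratio distance ln(0.84/1.20) = ln(0.70) = −0.3567, one-sided alpha 0.025 and power 80%:

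events = 4 × (1.960 + 0.842)² / 0.3567² ≈ 247, as stated in protocol 12.8.

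Power = Φ(√events / 2 × 0.3567 − 1.960). The share of patients who would be removed is not in the documents. Assuming a range, with events lost in proportion:

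| Assumed share removed | Patients of 2001 | Events left | Power |
|---|---|---|---|
| 0% | 0 | 247 | 80.0% |
| 1% | 20 | 244.5 | 79.6% |
| 2% | 40 | 242.1 | 79.2% |
| 5% | 100 | 234.6 | 78.0% |
| 10% | 200 | 222.3 | 75.8% |

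This shows the precision cost at the planned size only. It does not measure bias, which depends on who is removed from which arm.

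**The case against.** The best defence is that the criteria are the ones in sections 7.2 and 7.3, and each states one rule: a 2-week window and one LVEF list. Section 8.5 defers to the criteria, and footnote e annotates a schedule. Both medication rules can be met together by observing the longer, so sites are not given impossible instructions. This largely stands. A reader might infer that membership of the analysis set turns on which passage is read; the documents do not establish that. What remains is that 8.5 attributes to the criteria a rule they do not contain, and that the SAP itself carries the wider LVEF list.

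A reader might also infer that the SAP requires removal for a drug taken after randomisation. It does not say so. Table 1 places the eligibility check at screening/enrolment only, section 9.1 requires the criteria to be met there, and a later drug can be read as a deviation. The wording of exclusion 10 leaves the other reading open, and nothing in the SAP closes it.

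Protocol 12.2 does open by defining an included patient as one who met all criteria, and 12.12 allows exceptions where specified. But 12.2 then defines the primary efficacy population without that condition, and 12.2.1 rules out violations as a ground for exclusion.

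Finally, the sponsor ended the study early (SAP 2.4 and section 6), and SAP 5.4.4 treats the secondary endpoints as reference only. That lowers the stakes for the H/M ≥1.6 comparison. It does not affect the primary test, which SAP 5.4.2 still runs on the filtered set.

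**Conclusion.** The full analysis set in SAP 4.1.2 is wrong as written: it contradicts protocol 12.2 and 12.2.1 and, taken literally, removes randomised patients from an intention-to-treat primary analysis. This holds whichever medication window or LVEF list applies. The eligibility inconsistencies are secondary. They make the filter harder to apply consistently, but clearing them up would not cure the conflict over the analysis set and can no longer change who was enrolled.

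The number of patients affected cannot be derived from the documents. The loss of power, from 80.0% to between 79.6% and 75.8%, rests on an assumed 1% to 10% removal, events lost in proportion and the planned 247 events, which early termination makes illustrative only. The main issue is the integrity of the randomised comparison.

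**What to change.** In SAP 4.1.2, define the full analysis set as all randomised patients, analysed in the arm assigned, with no eligibility condition and no dependence on the safety set, as protocol 12.2 states. This also settles the post-randomisation reading of exclusion 10 for the efficacy analyses, since no criterion could then remove a randomised patient.

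Separately, reconcile exclusion 10 (protocol 7.3 and synopsis) with section 8.5, and inclusion 6 and section 9.1 with Table 1 footnote e in both protocol and SAP, so that each point has one rule. Which medication window or LVEF method is right is not for this review to say.

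The cost is wording only. SAP section 1 places sign-off before database lock, so the change to the analysis set belongs there.

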7.4 Withdrawal and Termination Criteria

7.4.1 Patient Withdrawal

There are no formal withdrawal criteria for this study. During the conduct of the study, the Sponsor may review the safety data for trends and signals that would indicate the need for withdrawal of a patient.

In accordance with the Declaration of Helsinki, each patient is free to withdraw from the study at any time. Investigator(s) also have the right to withdraw patients from the study in the event of illness, AEs, or other reasons concerning the health or well-being of the patient, or in the case of lack of co-operation.

Should a patient decide to withdraw after administration of AdreView™, or should the investigator(s) decide to withdraw the patient, all efforts will be made to complete and report the observations up to the time of withdrawal as thoroughly as possible. A complete final evaluation at the time of the patient's withdrawal should be made and an explanation given of why the patient is withdrawing or being withdrawn from the study. As this is an intention to treat analysis, all patients should be followed for the primary endpoint of all-cause mortality if at all possible. ICD crossover or having a secondary endpoint is not a reason to withdraw from the study.

The reason for withdrawal must be noted in the electronic Case Report Form (eCRF). If the reason for withdrawal is a serious adverse event (SAE), monitoring will continue until the outcome is evident. The specific event or test result(s) must be recorded in the eCRF. The reason for withdrawal must be noted in the eCRF. If the reason for withdrawal is a clinical AE, monitoring will continue until the outcome is evident. The specific event or test result(s) must be recorded in the eCRF. Patients withdrawing prior to completing the study may be replaced.

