8 TREATMENT OF PATIENTS

8.1 Investigational Medicinal Product (IMP)

8.1.1 AdreView™ (Iobenguane I¹²³ Injection)

After randomisation to either the AdreView™ group or the SoC group, all patients will receive at least one intravenous injection of 10 mCi (370 MBq) of AdreView™. A $\pm 10\%$ tolerance of the nominal dose will be allowed, thus yielding an acceptable dose range of 9 to 11 mCi (333 to 407 MBq) in accordance with the Package Insert/Summary of Product Characteristics/Investigator's Brochure (IB). AdreView™ will be administered in a volume of 5 mL (diluted using 0.9% sodium chloride as needed) and injected as a slow infusion over 1 to 2 minutes followed by 10 mL of saline flush injected over a maximum of 5 seconds. An administration volume of up to 15 mL may be used at sites where there are logistical limitations to achieving delivery of IMP within the timelines required to meet the $370 \pm 10\%$ MBq dose in a volume of 5 mL.

Patients being allocated to the AdreView™ low-risk group will receive a second injection of AdreView™ and planar /SPECT imaging 2 years (± 30 days) after the first one. If any of these patients voluntarily withdraw prior to completion of the study they will be offered this second AdreView™ scan prior to withdrawal being effective.

Refer to the Package Insert/Summary of Product Characteristics/IB and Appendix [15.2](#) for further detail.

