9.5 Second AdreView™ Administration

Patients in the low-risk AdreView™ group will undergo a second AdreView™ scan (planar and possibly SPECT) 2 years post-randomisation for purposes of re-stratification. All female patients will undergo a serum or urine pregnancy test unless pre-menarchal, surgically sterile or post-menopausal prior to this scan. Should the H/M ratio fall under 1.6 and the patient is willing and eligible for ICD implantation, he/she should receive an ICD. Should the patient withdraw prior to study termination the second AdreView™ scan will be offered prior to said withdrawal being effective.

- AEs, SAEs and AdreView™-emergent AEs will be recorded
- All data related to primary and secondary endpoints will be collected
- Injection site monitoring will be performed before and after injection (with findings recorded pre-administration, 15 minutes post-administration, and at discharge from the imaging suite)

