9.6 End of Study Visit

This will be an event-driven study. Patients will be enrolled and followed up until sufficient endpoints have accrued (247 primary endpoint events). All patients will then attend an end-of-study visit within 1 month.

If a patient discontinues prematurely, he/she will attend an end of study visit at that time. As this is an intention-to-treat analysis, all patients should be followed for the primary endpoint of all-cause mortality if at all possible.

The following parameters will be collected:

- Medical history (with identification of study end-points)
- Concomitant medications
- Vital signs (blood pressure, heart rate, respiratory rate, and pulse oximetry)
- A brief physical examination will be performed.
- AEs, SAEs and AdreView™-emergent AEs
- All data related to primary and secondary endpoints
- ICD interrogation (for those patients with an ICD); may be performed remotely within ±5 days of follow-up visit.

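### Protocol 8.5 lets an interfering drug end study participation, not just the scan; after the first scan this reason exists only for AdreView low-risk patients, which puts non-fatal endpoints at risk of one-sided loss

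*Protocol*

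**What the plan says.** Protocol 8.5 bars drugs that interfere with imaging for a period before AdreView is given. Where such a drug is needed and cannot be paused, "the investigator may elect to withdraw the patient from the study on safety grounds". The withdrawal is from the study, not from the scan.

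The scans come after randomisation. Protocol 8.1.1: "After randomisation to either the AdreView™ group or the SoC group, all patients will receive at least one intravenous injection". Protocol 9.3: "The first AdreView™ administration should be performed in the 15 (+7) days post-randomisation". The second scan belongs to one subgroup of one arm. Protocol 9.5: "Patients in the low-risk AdreView™ group will undergo a second AdreView™ scan (planar and possibly SPECT) 2 years post-randomisation". Table 1 heads that column as the low-risk cohort only.

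On what follows withdrawal, Protocol 7.4.1 says: "As this is an intention to treat analysis, all patients should be followed for the primary endpoint of all-cause mortality if at all possible". Section 9.6 repeats this and adds: "If a patient discontinues prematurely, he/she will attend an end of study visit at that time". Neither section asks for non-fatal endpoints to be collected after that visit.

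The SAP censors event-free patients at the last known-alive date for the arrhythmia composite (5.4.3.1) and syncope (5.4.3.2). It compares both hospitalisation endpoints by a Cochran-Mantel-Haenszel odds ratio (5.4.3.1). Missing values are not imputed (Protocol 12.5.3, SAP section 5).

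**The concern.** A rule written to protect image quality can remove a randomised patient from follow-up. At the first scan it applies to both arms. At 2 years it can apply only to AdreView patients from whom the ICD was withheld, because no SoC patient is due a scan. An SoC patient taking the same drug stays in the study.

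Two things could suffer. Deaths after withdrawal might be missed in one arm of a mortality comparison. Admissions, arrhythmias and syncope after withdrawal would go uncollected in that arm while the analysis carried on as if the patient had been observed. For non-inferiority comparisons at a margin of 1.20, missing events in the experimental arm is the undesirable direction.

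**Working it through.** **1. Reproducing the plan (Protocol 12.8).** Events = 4 × (1.960 + 0.842)² / [ln(0.84/1.20)]² = 246.8, so 247. With AdreView 36-month survival of 1 − 0.1134 = 0.8866 and SoC survival of 0.8866^(1/0.84) = 0.8665, the mean death probability is 0.12345, and 247/0.12345 = 2000.9, so 2001. (The rounded survival of 0.887 gives 2008.) Neither figure needs an allowance for loss to follow-up to be reproduced.

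**2. Patients exposed to the year-2 route.** Inputs are the table in 12.8 and the 1:4 LVEF mix.
- Low-risk share: 0.2 × 0.21 + 0.8 × 0.25 = 0.242. Per arm: 0.242 × 1000.5 = 242.
- Low-risk 36-month mortality: (0.042 × 9.72% + 0.200 × 4.68%) / 0.242 = 5.55%.
- Monthly hazard: −ln(1 − 0.0555)/36 = 0.00159. Alive at month 24: 242.1 × exp(−24 × 0.00159) = 233.
- Low-risk deaths after month 24, whole subgroup: 3.3 by month 33 and 4.4 by month 36 (2.75 to 3 years, Protocol 6.3).

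**3. Primary endpoint, if vital status is not obtained.** The share withdrawn is not in the documents. I assume 2% to 20% of the 233 (5 to 47 patients), with a hazard m = 1 to 3 times the low-risk hazard.
- Deaths lost: e = number withdrawn × [1 − exp(−m × 0.00159 × (F − 24))], where F = 33 or 36 months.
- Expected HR = [(E − e) / (T − t)] / λ(SoC). E and T are AdreView deaths and person-months, t is the lost person-months, and λ(SoC) = [−ln(0.887)/36] / 0.84 = 0.00397 per month.
- At F = 36, E = 113.1 and T = 33,942. With 20% withdrawn:
  - m = 1: e = 0.88 and HR = 0.847.
  - m = 3: e = 2.59 and HR = 0.834.
- Over the whole grid, 0.1 to 2.6 deaths are lost and the HR lies between 0.834 and 0.847, against 0.840 planned.
- The sign depends on who leaves. The break-even is m = 0.00333/0.00159, about 2.1. Below it the HR moves against AdreView, above it in favour.
- With 32-month accrual and every patient followed to month 72, up to 6.6 deaths are lost and the HR is 0.830 to 0.853. That case expects about 369 deaths, beyond the 247 that trigger the analysis, so it is an outer bound.

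If vital status is obtained, e = 0 and the HR stays at 0.840.

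**4. Non-fatal endpoints.** I assume 5% to 15% of 233, which is 11.7 to 35.0 patients, each with 0.75 to 1 year left after month 24.
- *Arrhythmia composite and syncope.* If vital status is still collected, the last known-alive date runs past the end of endpoint collection. The unobserved time is 11.7 × 0.75 = 8.8 to 35.0 × 1 = 35.0 patient-years. The AdreView arm has about 2606 patient-years at 33 months and 2828 at 36, so this is 0.3% to 1.2% of the arm's time. If the missed event rate equals the arm's average, the HR is pulled down by about that percentage; at k times the average, by k times as much. The pull is always towards AdreView.
- *Hospitalisation.* The odds ratio takes no account of length of follow-up. A patient withdrawn at year 2 without an earlier admission can count as a non-event. The ceiling, if every such patient would later have been admitted for the first time, is 12 to 35 of 1000.5, or 1.2% to 3.5% of the arm. The documents do not give the rates needed for a central estimate.

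**The case against.** Several points on the other side stand.

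- Section 8.5 is permissive and starts from the exclusion criteria, so it can be read as an entry and first-scan rule that treats both arms alike. No passage says that a missed 2-year scan leads to withdrawal, and Table 1 footnote f already exempts low-risk patients who have received an ICD. Even so, nothing in 8.5 confines it to the first scan, and that scan also follows randomisation. The ambiguity is a reason to clarify.
- Section 7.4.1 gives investigators a general right to withdraw patients in either arm. Only the scan-related reason is one-sided.
- All randomised patients are analysed as randomised (Protocol 12.2), and mortality follow-up after withdrawal is requested.
- The SAP reports early termination and treats secondary results as reference only (2.4, 5.4.4). It does not say how many patients reached year 2.

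A reader might go further and infer that the patients who leave are the sicker ones, so that their loss flatters AdreView on mortality. The documents do not support this. The interfering drugs listed in exclusion criterion 10 include antidepressants, so being unable to pause one need not mean a worse cardiac prognosis. The HR calculation also moves in both directions.

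**Conclusion.** The point holds as a risk of differential loss, mainly for hospitalisation, the arrhythmia composite and syncope. A reader might conclude that follow-up is lost in one arm. That is too strong: the rule is optional, mortality follow-up is requested in 7.4.1 and 9.6, and no deaths need be lost.

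The primary endpoint is little affected: the HR shifts by about 0.007 or less at planned follow-up, assuming 2% to 20% withdrawn, one to three times the low-risk hazard, and no vital status at all. For the non-fatal endpoints the effect is also modest if 12 to 35 patients are involved, but its direction is known. Uncollected events can only be missing from the AdreView arm, and the SAP's censoring date and odds ratio both count the gap as event-free. Early termination lessens the practical weight without removing the issue for patients who reached year 2.

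**What to change.** - **Protocol 8.5 and 7.4.1.** Reconcile 8.5 with the intention-to-treat statements in 7.4.1 and 9.6. State that a scan omitted for drug interference, in particular the 2-year scan, is not in itself a reason to end study participation, as 7.4.1 already says of ICD crossover. Where consent allows, all visits and endpoint collection continue in the assigned arm, and the reason for the missed scan is recorded.
- **SAP 5.4.3.** Censor non-fatal endpoints at the last endpoint assessment instead of the last known-alive date.
- **SAP 5.2.** Report scan-related withdrawals by arm and time, so that readers can judge the imbalance, including its effect on the hospitalisation odds ratios.

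This leaves medication, and how the ICD decision is made when the first scan cannot be done, to the sponsor and investigators. The cost is a few sentences. The visits are already scheduled, and the downside is a few patients without an H/M or re-stratification value.
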